
Study Procedures
	
The study visits include baseline visit, admission (surgery to discharge), and follow-up visit after discharge:
 
 
- Baseline: To determine study eligibility and collect baseline information (demographics, medications, medical history, surgical history, etc.)
 
- Surgical procedure: To re-confirm eligibility criteria, procedure set-up and take-down, medication changes, intraoperative complication evaluation, disease state evaluation, procedure success, conversion rates, protocol deviation, adverse event evaluation, and device deficiency collection
 
- Up to hospital discharge: Adverse event evaluation, complication rate, disease state evaluation, medication changes and protocol deviation
 
- Follow-up after discharge: Adverse event evaluation, complication rate, disease state evaluation, length of hospital stay, readmission (if applicable), reoperation (if applicable), medication changes, protocol deviation and study exit
 
 
Prior to subject enrollment, investigators who participate in surgical procedure will be properly trained on the investigational device. When a subject provides written informed consent, the principal investigator reviews the subject's medical records and confirms the eligibility criteria. The subject will be hospitalized and prepped for surgery according to site standard practices. On the day of surgery (Day 0), robot-assisted prostatectomy or cholecystectomy using Hugo™ RAS System is performed according to patient's indication. Intraoperative complication during the surgery will be monitored. For prostatectomy subjects, pathological examination on the resected specimen shall be performed.

	
Subjects will be followed through 30-day post-operative visit. Prostatectomy subjects will be followed at the day of discharge, 7-, 14-, and 30-day post-operative visits. Cholecystectomy subjects will be followed at the day of discharge, and 30-day post-operative visit. Post-operative complications will be evaluated. Subject’s study participation will be terminated when the subject expires, is lost to follow-up, or at the last follow-up visit (whichever occurs first).
																	

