## 8.7. Post-Operative Follow-up (Up to Day 30)

Subject will be followed through 30-day post-surgery.

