## 8.8. Subject Exit, Withdrawal or Discontinuation

Subjects have the right to refuse to participate the study as well as voluntarily withdraw from the study at any time. In case of study exit, the reason and date for study exit of all enrolled subjects will be documented on the applicable page of case report form (CRF). Subjects may be exited from the study for any of the following situations:

- Study completed (i.e., completed 30-day post-operative visit)
- Subject did not provide consent
- Subject chooses to withdraw
- Subject did not meet inclusion/exclusion criteria
- Subject did not receive surgery using the investigational device
- Subject death
- Subject lost to follow-up (i.e., up to 30-day post-operative visit)
- Unacceptable AEs
- Investigator deems withdrawal necessary (e.g., medically justified, failure of subject to maintain adequate study compliance)

All AEs must be followed until the AE has been resolved, is unresolved with no further actions planned, the subject dies or exits the study, whichever occurs first. In cases of early study exits, all data collected from the time of consent to the time of exit may be used. For subjects who complete the 30-day follow-up visit, the 30-day follow-up visit and exit visit should be combined, and CRF for both need to be completed.

*Medtronic Business Restricted*

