## 8.11. Assessment of Safety

Safety will be assessed by monitoring the occurrence of Aes and DDs. AE assessments will take place starting with the point of consent through study exit and will be recorded in the CRF. The secondary endpoints of this study (i.e., complication rate and readmission/reoperation rate (through 30-day post-surgery), DD rate) will assess the safety of the investigational device. See Section 10 for further information on the collection of safety information.

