## 8.13. Deviation Handling

A study deviation is defined as an event within a study that did not occur according to the Clinical Investigation Plan (CIP) or the Clinical Trial Agreement (CTA). Prior approval by the sponsor of deviation is expected unless when a deviation is necessary to protect the safety, rights or well-being of a subject in an emergency or in unforeseen situations beyond the investigator's control (e.g., subject failure to attend scheduled follow-up visit, inadvertent loss of data due to computer malfunction, inability to perform required procedures due to subject illness). All study deviations must be reported on the CRF regardless of whether medically justifiable, preapproved by the sponsor, an inadvertent occurrence, or taken to protect the subject in an emergency.

In the event the deviation involves a failure to obtain a subject's consent, or is made to protect the life or physical well-being of a subject in an emergency, the deviation must be reported to the IRB as well as sponsor within five working days. All other study deviations must be reported to the sponsor as soon as possible upon the study site becoming aware of the deviation, per IRB policies and/or local laws.

The sponsor is responsible for analyzing deviations, assessing their significance, and identifying any additional corrective and/or preventive actions (e.g., amend the CIP, conduct additional training, terminate the investigation). Repetitive or serious investigator compliance issues may result in initiation of a corrective action plan with the investigator and study site, and in some cases, may necessitate suspending enrollment until the problem is resolved or ultimately terminating the investigator's participation in the study.

Examples of major study deviations include but are not limited to:

- Failure to obtain proper IC
- Subject did not meet Inclusion/exclusion criteria
- Failure to collect required study data up to 30-day post-surgery

Other minor deviations shall be recorded along with reason for deviation. Subjects with minor deviation only may not be excluded from the final analysis unless the deviation affects the study outcome.

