## 10. Adverse Events and Device Deficiencies

### 10.1. Adverse Events and Device Deficiencies

All AEs will be collected throughout a subject's participation, starting from the time the IC is provided, regardless of their severity or relationship to the Hugo™ RAS or study procedures. Assessment of the occurrence of an AE will be based on changes in the subject's physical examination, laboratory results, and/or signs and symptoms. Reporting of these events to the sponsor will occur on an AE CRF, including date of AE, event description, treatment, resolution, assessment of both the seriousness of the AE and the relatedness to the system components. The completed AE CRF must be submitted to Medtronic as soon as possible.

In addition, DD information will be collected throughout the study and reported to the sponsor on a DD CRF. Note that DDs that result in an AE to the subject should be captured as an AE only. DD that could have led to a serious adverse device effect (SADE) (i.e., if suitable action had not been taken, if intervention had not been made, or if the circumstances had been less fortunate) require immediate reporting.

Upon receipt of AE or DD at Medtronic, a sponsor representative will review the AE/DD for completeness and accuracy and when necessary will request clarification and/or additional information from the investigator. If the event is unanticipated or unanticipated serious ADE, the sponsor will review the specific details behind those observations and determine what, if any, action is appropriate.

For any changes in status of a previously reported AE or DD (i.e., change in actions taken, change in outcome, change in relatedness), information needs to be updated on, or added to the original AE or DD CRF.

All AEs must be followed until the AE has been resolved, is unresolved with no further actions planned, the subject dies or exits the study, whichever occurs first. At the time of study exit, all collected AEs that are unresolved must be reviewed and an update to the original AE must be reported.

Adverse events that have not resolved at the time of the subject's discontinuation or completion of the study should have an outcome of Not Recovered/Not Resolved at study end in subject source and on eCRF. The investigator should ensure that subject is aware of any follow-up or additional treatment that is required for any ongoing AE at the end of study participation; however, there will be no eCRF entry for the ongoing follow-up.

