7.1.3 Analysis Sets

The following populations will be considered for the analysis of data for this study:

- Full Analysis Set (FAS): The Full Analysis Set is defined as all enrolled subjects in whom the Hugo™ RAS procedure is begun (defined as the first skin incision). In the event that a subject is consented but the first incision does not occur (e.g., if the subject becomes ineligible during the timeframe between consent and the procedure day), that subject will be excluded. Also, a subject who inevitably converted (to open or conventional laparoscopic surgery) not due to the Hugo™ RAS system will be included in the safety and other descriptive analyses but excluded from the primary endpoint analysis (since the subject is not evaluable).
- Per Protocol Set (PPS): The per protocol set is a subset of the FAS including only those without any major protocol deviations. Following subjects from the FAS will be excluded from the PPS:
 - Subject who inevitably converted (to open or conventional laparoscopic surgery) not due to the Hugo™ RAS system
 - Subject did not meet Inclusion/exclusion criteria
 - Subject chooses to withdraw
 - Failure to collect required study data up to 30-day post-surgery

The FAS will be the primary analysis set for the evaluation of the primary and secondary endpoints. Statistical analysis will be performed for each analysis set. However, if all subjects complete the study per the CIP, the results can be presented regardless of the analysis set. Subject disposition will be illustrated in a CONSORT diagram. All enrolled subjects will be included in a subject disposition table indicating reasons for exclusion from the FAS and PPS analysis sets.

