7.9 Evaluation of Objectives

Study objectives will be assessed through study endpoints measurement.

- Primary Endpoint

The primary objective is to confirm that the Medtronic Hugo™ RAS System performs as intended when used for prostatectomy or cholecystectomy. Primary endpoint is below:

- Completion rate: A proportion of subjects who completed the surgery without conversion (to open or conventional laparoscopic surgery) due to system serious malfunction, and without any major complications within 24-hour post-surgery (Major complication is defined as Clavien-Dindo grade ≥ 3)

The number of subjects successfully completed the surgical procedure, percentage, and its Clopper-Pearson Exact 95% confidence interval will be summarized. If the point estimate of the completion rate is greater than or equal to the pre-determined value (i.e., 0.95), it is considered that the primary objective is met. This primary endpoint will be assessed on overall subjects and according to surgery performed (prostatectomy and cholecystectomy).

- Secondary Endpoints

The secondary objective is to assess the short-term safety outcome of the Medtronic Hugo™ RAS System when used for prostatectomy or cholecystectomy. Secondary endpoints are below:

- Overall complication rate through 30-day post-surgery: A proportion of subjects with any postoperative complication within 30-days post-surgery using the investigational device
- Major complication rate through 30-day post-surgery: A proportion of subjects with any postoperative complication classified ≥ 3 by the Clavien-Dindo system within 30-days post-surgery using the investigational device
- Readmission rate through 30-day post-surgery: A proportion of subjects hospitalized within 30 days post-surgery
- Reoperation rate through 30-day post-surgery: A proportion of subjects go through reoperation for the same indication within 30 days post-surgery
- Device deficiency rate: A proportion of subjects with any device deficiency (DD) during robotic assisted surgery using the investigational device

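### The final visit may fall on Day 23 and ends data collection, so four 30-day safety rates can miss up to the last seven days

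*Protocol*

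**What the plan says.** **Horizon.** Protocol 4.2.2 and SAP 7.9 define four secondary rates over 30 days: overall complications, major complications (Clavien-Dindo grade 3 or higher), readmission and reoperation. Readmission, for example, is "A proportion of subjects hospitalized within 30 days post-surgery". Protocol 8.7 opens with "Subject will be followed through 30-day post-surgery".

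**Visit window.** Protocol Table 5 and sections 8.7.1 and 8.7.2 set the last visit at Day 30 ±7 days for both procedures. For cholecystectomy subjects it is the only scheduled visit after discharge.

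**Exit.** Section 8.8 treats a subject who has had that visit as having completed the study, and adds: "For subjects who complete the 30-day follow-up visit, the 30-day follow-up visit and exit visit should be combined". The Synopsis (Study Procedures) says that "study participation will be terminated when the subject expires, is lost to follow-up, or at the last follow-up visit (whichever occurs first").

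**End of data collection.** Section 8.11: "AE assessments will take place starting with the point of consent through study exit and will be recorded in the CRF". For events still open at exit, section 10.1 says "there will be no eCRF entry for the ongoing follow-up".

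**Analysis.** SAP 7.1.3: "The FAS will be the primary analysis set for the evaluation of the primary and secondary endpoints". Membership of the FAS depends on first skin incision, not on length of follow-up. Each rate is a simple proportion with a Clopper-Pearson interval (SAP 7.9). SAP 7.4 imputes nothing in the primary analysis and makes sensitivity analysis optional.

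**Partial safeguard.** Section 8.13 lists "Failure to collect required study data up to 30-day post-surgery" as a major deviation. Protocol 9.1 and SAP 7.1.3 make the same failure a reason for exclusion from the PPS.

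**The concern.** A symmetric window does no harm when events are ascertained to the endpoint's horizon whatever the visit date. Here the visit date is also the end of ascertainment, and half of the window lies before the horizon. The early and late halves do not cancel: an event after Day 30 falls outside the definitions, so a late visit adds nothing to offset what an early visit loses. The error can only lower the rates, and how much is lost depends on when appointments happen to be booked.

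These four rates carry most of the secondary safety objective of a 40-subject pivotal trial. SAP 7.9 also reports them within each procedure, where there are 20 subjects and one subject is 5 percentage points.

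**Working it through.** **Inputs from the documents.** N = 40, 20 per procedure (Protocol 7.2); last visit at Day 30 ±7 (Table 5); horizon 30 days (SAP 7.9).

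**Inputs that must be assumed.** The documents give no distribution of visit dates, no expected complication rate and no timing of events. I use two visit patterns (evenly spread over the window; everyone on the first permitted day), true 30-day rates of 10% and 30%, and a constant event rate over the 30 days.

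**1. Window.** 30 − 7 = 23 and 30 + 7 = 37, so there are 15 permitted days, of which 7 (Days 23–29) precede Day 30. A compliant subject can lack 1 to 7 days, at most 7/30 = 23.3% of the horizon.

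**2. Unobserved time.**
- No early visits: 0 of 40 × 30 = 1,200 subject-days.
- Even spread: 40 × 7/15 = 18.7 subjects exit early. Lost time is 40 × (7+6+5+4+3+2+1)/15 = 74.7 subject-days, and 74.7/1,200 = 6.2%.
- All on Day 23: 40 × 7 = 280 subject-days, and 280/1,200 = 23.3%.

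**3. Expected subjects missed.** With a constant rate, the chance of being event-free to day d is (1 − p)^(d/30). A subject who exits on day d < 30 has a first event between d and Day 30 with probability (1 − p)^(d/30) − (1 − p). For p = 10% and d = 23 this is 0.9224 − 0.9000 = 0.0224. For the even spread, sum over d = 23 to 29, divide by 15 and multiply by 40.

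| True 30-day rate | Even spread, Days 23–37 | All on Day 23 |
|---|---|---|
| 10% | 40 × 0.0893/15 = 0.24 subjects (0.6 points) | 40 × 0.0224 = 0.90 subjects (2.2 points) |
| 30% | 40 × 0.2401/15 = 0.64 subjects (1.6 points) | 40 × 0.0607 = 2.43 subjects (6.1 points) |

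**4. If events cluster early.** Suppose only 5–10% of events fall after Day 23 and every subject exits on Day 23. At a true rate of 10% (4 expected events in 40), the loss is 4 × 0.05 = 0.2 to 4 × 0.10 = 0.4 subjects.

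**5. What one missed subject does.** It moves a rate by 1/40 = 2.5 points overall or 1/20 = 5 points within a procedure. Exact 95% upper limits:

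| Events | n = 40 | n = 20 |
|---|---|---|
| 0 | 8.8% | 16.8% |
| 1 | 13.2% | 24.9% |

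These limits show how sensitive so small a sample is to a single event. They do not measure how often an event would be missed.

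**The case against.** The strongest counter-argument is about weight. SAP 7.5 calls the primary and secondary analyses descriptive, the secondary rates have no success rule, and the 24-hour primary endpoint cannot be affected. The likely bias is well inside the sampling error: the exact interval for 0 of 40 already reaches 8.8%. Every magnitude above rests on assumed visit dates, rates and timing, and a constant rate probably overstates late events after surgery. All of this stands, and it limits the importance of the point.

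It can also be said that the plan already requires 30 days. Protocol 7.2 and 8.7 speak of 30 days of follow-up, and missing data up to that day is a major deviation. Read that way, ±7 is only a scheduling tolerance. But no text requires contact on or after Day 30 for a subject seen earlier in the window, and none says whether an in-window visit on Days 23–29 is such a deviation. If it is, subjects who kept their appointment become major deviators. If it is not, nothing guards the gap. In either case the rule acts on the PPS and leaves the FAS, the primary set, as it was.

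Other provisions help less than they seem to. Unscheduled visits (Table 5, note 1) and telephone contact (section 12.17) are permitted but not required. SAP 7.1.1 summarises the analysis sets by follow-up but sets no Day 30 cut-point. The multiple imputation mentioned in SAP 7.4 is optional and leaves the main proportion unchanged.

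Two limits on the evidence are fair. That early leavers count as event-free is an inference: no sentence says so, but it is what a proportion of FAS subjects with an event yields when nothing deals with short follow-up. The section 10.1 sentence on open events is peripheral, since those subjects already count in the overall complication rate. It bears only on later worsening, readmission or reoperation.

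**Conclusion.** The concern holds. Followed exactly, the visit window and the exit rule let a compliant subject leave 1 to 7 days before the horizon of four secondary safety rates, and the analysis makes no allowance for it. The direction is certain: any error under-counts harm. The size is unknown but probably less than one subject in 40. The evenly spread case gives 0.24 to 0.64 subjects for assumed rates of 10% to 30%, fewer if events cluster early. Everyone exiting on Day 23 gives 0.9 to 2.4, under a constant event rate. With no early visits the loss is zero.

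The trial's success decision and the device deficiency rate do not change. The gain is safety rates that mean what their definitions say, at little cost, so the change should be made.

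**What to change.** - **Protocol 8.8:** state that no subject is recorded as having completed the study before Day 30. For a visit on Days 23–29, confirm adverse event, readmission and reoperation status through Day 30 by telephone or record check, then exit the subject. The alternative is to set the final data window to Day 30–37 in Table 5, 8.7.1 and 8.7.2.
- **Protocol 8.13 and 9.1, SAP 7.1.3:** say whether an in-window visit before Day 30 without that check counts as failing to collect data up to 30 days.
- **SAP 7.9:** report the number of FAS subjects observed to Day 30, overall and by procedure, beside each 30-day rate.

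The cost is wording in the protocol, CRF and SAP, plus either a short call or record check for subjects seen early or a few later appointments.

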**CONFIDENTIAL**

056-F275 Rev E Clinical Investigation Plan Template

### 8.9. Prior and Concomitant Medications/Therapies

There is no prohibited medication during the study, and the investigator shall follow institutional standard of care to manage medications. Follow the guidelines below to report medications relevant to this study:

- Report applicable pre-procedure medications if taken within 30 days of the study procedure as listed Table 6
- Any relevant medication related to the study indication
- Pain medication(s) must be reported if given when pain (Clavien Dindo Grade 1 or higher – pain exceeds that which is considered within normal limits) is reported as an AE
- Medications given as treatment for an AE should be captured

**Table 6. Medications Taken within 30 Days prior to Surgery**

Anticoagulants taken within 30 days prior to surgery	Monoamine Oxidase Inhibitors (MAOIs) taken within 30 days prior to surgery

 
• Warfarin (Coumadin)
 
• Enoxaparin (Lovenox)
 
• Clopidogrel (Plavix)
 
• Ticlopidine (Ticlid)
 
• Aspirin (in many versions)
 
• Non-steroidal anti-inflammatory (NSAIDS) (in many versions)
 
• Dipyridamole (Persantine)
 
• Vitamin E
 
• Garlic
 
• Ginger
 
• Ginkgo biloba
 
 and other anticoagulants not mentioned above	
 
• Tranylcypromine (Parnate, Sicoton)
 
• Phenelzine (Nardil, Nardelzine)
 
• Isocarbozid (Marplan)
 
• Rasagiline (Azilect)
 
• Selegiline (Eldepryl, Deprenyl)
 
• Linezolid (Zuvon) (an antibiotic)
 
• St. John’s Wort
 
 and other MAOIs not mentioned above

Exclude the reporting of antiemetics, antipyretics, analgesics, diuretics, electrolytes, antibiotics, digestives, antitussives, expectorants, physiotherapy and so forth when given per standard of care procedures and/or within normal limits (dosage and frequency).

All collected medications will be coded using WHO Drug Dictionary.

### 8.10. Assessment of Effectiveness

Effectiveness of the Hugo™ RAS System will be evaluated through the study primary endpoint (completion rate). Effectiveness assessment will be done on the day of surgery as below.

*Medtronic Business Restricted*

- Completion rate: A proportion of subjects who completed the surgery without conversion due to system serious malfunction, and without any major complications within 24-hour post-surgery

Surgery completion is defined if procedure is completed without conversion to open or laparoscopic surgery due to system serious malfunction per surgery record, and no major complication reported within 24-hour post-surgery period. Note that unavoidable Aes are inherent to the procedure (see Section 10.2 for details) are not included in this definition of major complication within 24-hour post-surgery.

